### 3 Trial Design

The study will be a non-randomized experimental design with 3 phases. First, data about current practices will be collected before interventions begin. Second, we will pilot the mechanics of delivering the report card while educating users about it. Third, we will measure handoff and usability outcomes on alternating days with and without the intervention. (2:1 intervention to non-intervention). We anticipate the number of intervention-deliver and education days to be 30, but may have to periodically update the report card delivery requiring an additional delivery-testing period. During the entire study, we will accept and record any safety concerns from participants.

#### **Methods**

### 4 Participants, Interventions, Outcomes

### 4.1 Study Setting

This will be a single center, non-randomized clinical trial at Barnes Jewish Hospital (BJH) in St. Louis, a large tertiary care academic medical center affiliated with Washington University in St Louis (WUSTL).

### 4.2 Participants and Eligibility

#### 4.2.1 Inclusion criteria

• Adults undergoing OR procedures in BJH South campus, including all of "Pod 2", "Pod

- 3", "Pod 5" and excluding all procedure suites such as Interventional Radiology, Parkview Tower "Pod 1", Center for Advanced Medicine "Pod 4", Labor and Delivery suites.
- Surgical service is "Acute and Critical Care Surgery", Otolaryngology, Hepato-biliary, Vascular, or Abdominal Transplant
- Planned non-ICU disposition ("floor" and "observation unit" collectively "ward" patients).
- Calculated risk of unplanned ICU admission in the first 7 postoperative days in the top 15% of historical records.

Risk of unplanned ICU admission will use the same calculator currently employed in the ACT. Risk factors considered include the surgery performed, demographics, laboratory values, comorbidities, vital signs, and medications.

Although patients are exposed to effects of the intervention, data is obtained from healthcare providers. Included providers are PACU nurses, PACU anesthesiology physicians, wards nurses, and wards midlevel providers (resident physicians, physician assistants, and advanced practice nurses) who are involved in a postoperative handoff for these patients.

### 4.2.2 Durations and sample sizes

The planned duration and size of each phase is

- Pre-intervention observation: 60 working days, 50 patients
- Education and intervention delivery testing: 30 working days, 50 patients
- Intervention evaluation: 90 working days, 350 patients divided into 30 without-intervention days and 60 with intervention days.

The exact number of providers surveyed is difficult to project, because some providers will care for multiple patients, nurses and midlevel providers change their assignments, and staff turnover may occur. We anticipate surveying fewer than 60 distinct PACU RNs, fewer than 15 PACU residents, fewer than 20 PACU physicians, fewer than 60 distinct floor RNs, and fewer than 25 distinct midlevel providers.

### 4.2.3 Case screening and identification

Patients eligibility is pre-screened automatically, and a researcher or ACT clinician verifies their eligibility. The first two enrollment criteria

- Adults undergoing OR procedures in BJH South campus, including all of "Pod 2", "Pod 3", "Pod 5" and excluding all procedure suites such as Interventional Radiology, Parkview Tower "Pod 1", Center for Advanced Medicine "Pod 4", Labor and Delivery suites
- Surgical service is "Acute and Critical Care Surgery", Otolaryngology, Hepato-biliary Surgery, or Abdominal Transplant Surgery

are taken from the surgical schedule. The third enrollment criteria

- Planned non-IČU disposition ("floor" and "observation unit" collectively "ward" patients). is taken from (1) the procedure schedule request, (2) the anesthesiologist day-of-service anesthesia plan documentation, (3) a predictive model based on the scheduled surgery. Cases with > 75% likelihood of direct ICU admission or outpatient discharge are automatically excluded by the predictive model. The final criterion
  - Calculated risk of unplanned ICU admission in the first 7 postoperative days in the top 10% of historical records.

is calculated using the same model described in 4.3.2

[figure not shown]
Once the server has identified patients as likely eligible, they are marked for review in the ACT

ML dashboard, where final eligibility is confirmed.

During the intervention evaluation (phase 3), each day will be with or without intervention for all eligible patients. These will rotate 2:1 over work days, eg week 1 = (with, with, without, with, with), week 2 = (without, with, with, without, with), week 3 = (with, without, with, without)

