Communicating from the ACT to the PACU physicians presents several advantages. First, the ACT clinician is familiar with the general model of ML output generated by AlertWatch and will filter out obvious errors from reaching the care team and potentially harming the patient, minimizing risk to participants. Second, because on a given day a single attending physician and resident oversees the PACU at BJH South Campus, friction related to communication between the ACT and these providers will be minimized as these contacts become routine. Both parties will have the opportunity to rapidly adjust to the presence of the report card as they will process multiple such reports per day. Third, because the ACT-postop communication happens before formal handoff, it will allow these providers to look into higher risk cases before they arrive and ask more detailed questions during handoff. We anticipate that most interactions will consist of simply forwarding the report card. The ACT will not communicate directly to PACU nurses or ward providers.

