ML output will be generated on a server controlled by the investigators and administered by Washington University Information Technology. This is the same server and data access mechanism used by the ACT team. A feed of preoperative and intraoperative data extracted from the Epic EHR designed for use in the AlertWatch system is currently saved in a database maintained by BJH and exposed for authorized users to access, which we will access using encrypted transport mechanisms. The server will also have a TLS-encrypted and password protected web interface (dashboard) for debugging, message generation, and manual end-ofcase triggering. The web interface will allow study technical staff and ACT clinicians to look up current and previous risk profiles by study identifier, patient identifier and date, or date, time, and operating room number. It will also allow them to manually enter that a case is concluding, and to mark a day as "with-intervention". The study identifiers, date, time, end of case marker, intervention indicator, and ML output will be stored on the WUSTL Research Infrastructure Services Data Storage Platform. The RIS Data Storage Platform is a scalable distributed storage solution with an integrated long-term archive. It is institutionally approved for protected health information, and requires WUSTL-key authentication and 2-factor authentication outside WUSTL facilities. Data access is granted only on a per-user basis and logged. The ML server is behind the Washington University firewall and inaccessible from off-campus computers.

To avoid misleading postoperative providers, we will create a brief educational sheet explaining the purpose of the study and the items included in the risk profile (attached). The educational sheet will include the calibration accuracy and other appropriate metrics regarding the predictions. For example, at the screening threshold we will use the sensitivity for AKI is about 50%, meaning that the provider should not be falsely reassured by not receiving an alert. We will stress that these risk predictions were formed in the context of usual care at BJH, and that a

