#### 4.8 Allocation

Allocation is determined solely by entry time into the study.

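### In phase 3 a person who can be expected to know the day's predictable status makes the final eligibility decision, unmasked and with no rejection log, so patient selection could differ modestly between day types.

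*Combined protocol and SAP*

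**What the plan says.** Status is set for whole days. Section 4.2.3 says "each day will be with or without intervention for all eligible patients" and gives the pattern: "These will rotate 2:1 over work days, eg week 1 = (with, with, without, with, with". Section 4.8 adds: "Allocation is determined solely by entry time into the study". Section 3 describes the design openly as non-randomized.

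Selection has two steps. Section 4.2.3 says: "Patients eligibility is pre-screened automatically, and a researcher or ACT clinician verifies their eligibility". Patients flagged by the server go for review to the ACT "ML dashboard, where final eligibility is confirmed".

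Under section 4.3.1, the server's web dashboard lets study technical staff and ACT clinicians "manually enter that a case is concluding, and to mark a day as" a with-intervention day. The same section has a report card validated by hand before it prints, and section 4.3.5 says that no cards are generated for non-contact patients.

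Section 4.9 deals with the blinding of patients and treating clinicians only. Section 5.3 compares the two groups by chi-square and calls the primary analysis intention to treat. Section 4.3.4 allows the screening threshold to be changed if either provider group is overloaded.

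**The concern.** The main comparison is between with- and without-intervention days in phase 3. It is fair only if the same kind of patient is counted on both. An automatic screen alone would largely secure that. Here a human decision comes after the screen and settles who is finally eligible, and the person deciding can be expected to know the day's status.

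If harder handoffs are turned away more often on one day type, the acceptable-handoff rates will differ even when the report card does nothing. The direction cannot be predicted from the documents. The chi-square test has no means of correcting the imbalance. Without a record of rejected patients, readers could not see whether it occurred.

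**Working it through.** **1. The plan's own figures.** A with-with-without cycle over 90 work days has 90/3 = 30 cycles, so 60 with and 30 without days, as section 4.2.2 states. There are 90/5 = 18 of each weekday. Because 3 and 5 share no factor, each weekday meets each cycle position 6 times: 12 with and 6 without, if no holidays intervene. Weekday is therefore balanced, and the weakness is predictability.

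Section 4.5 gives 18 points as the detectable increase from 70% with 50 versus 100 patients at 80% power. A two-sided 5% test (assumed, since the plan states neither alpha nor sidedness) with pooled variance gives 18.9 points. The gap between 18 and 18.9 is a separate matter. At the 350 patients of section 4.2.2, split 2:1 (350/3 ≈ 117 and 233), the detectable difference is 13.2 points.

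**2. Does the verifier know the status?**
- ACT clinician: can mark the day in the dashboard and validates cards (4.3.1), and no cards are generated for non-contact patients (4.3.5). Knowledge is a strong inference.
- Researcher: likely, but no text says so.
- Timing: section 7.3 says that eligibility can be determined only once the patient has had anesthesia or sedation, so confirmation falls after the day's status is in force.

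**3. Where is there room for judgement?**
- Planned disposition comes from three sources with no stated rule for conflicts (4.2.3).
- The risk cut-off is the top 15% in 4.2.1 but the top 10% in 4.2.3, and Vascular is listed in 4.2.1 but not in 4.2.3. These passages must be reconciled.
- Section 4.3.4 names ACT staffing and alert fatigue as limits on contacts. That pressure arises on with-intervention days, and no rule makes a threshold change apply to both day types.

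**4. How large could the bias be?** The documents give no confirmation rates, so every input here except the 70% base (section 4.5) is assumed. Let hard handoffs be acceptable with probability p_h and the rest with p_e.
- Share of hard handoffs: h = (p_e − 0.70)/(p_e − p_h).
- A fraction f of hard handoffs is not confirmed on with-intervention days only. Their share there becomes h′ = h(1 − f)/(1 − hf).
- Bias = p_e − (p_e − p_h)h′ − 0.70.

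Example: p_e = 0.80 and p_h = 0.50 give h = 0.10/0.30 = 1/3. With f = 0.5, h′ = 0.1667/0.8333 = 0.20, the observed rate is 0.80 − 0.30 × 0.20 = 0.74, and the bias is 4.0 points.

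| p_e / p_h | h | f = 10% | 20% | 30% | 50% |
|---|---|---|---|---|---|
| 0.75 / 0.55 | 0.25 | 0.4 | 0.8 | 1.2 | 2.1 |
| 0.80 / 0.50 | 0.33 | 0.7 | 1.4 | 2.2 | 4.0 |
| 0.85 / 0.40 | 0.33 | 1.0 | 2.1 | 3.3 | 6.0 |

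Entries are bias in percentage points.

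Two-sided type I error, by exact enumeration of the chi-square test without continuity correction:
- Middle row, 50/100: 5.2%, 5.6%, 6.2% and 8.6%.
- Middle row, 117/233: 5.3%, 6.0%, 7.4% and 12.7%.
- Strongest cell (6.0 points): 13.2% at 50/100 and 22.9% at 117/233.

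A cruder calculation takes the share of all flagged patients dropped on one day type, times the outcome gap between dropped and kept patients. At 10% and 30 points it gives 0.10 × 30 = 3 points; at 20% it gives 6 points.

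**The case against.** The strongest reply is that little discretion is left. Patient recruitment is automatic (4.7) and patient consent is waived (7.3), so nobody chooses whom to approach and no patient refusal can vary by day. Location and service come from the surgical schedule, risk is computed, and cases with more than 75% likelihood of direct ICU admission or outpatient discharge are excluded by model (4.2.3). On with-intervention days every eligible patient is to be treated (Non-Technical Summary). The design does not claim to be randomized. All of this stands and is why the likely bias is small. It does not remove the point, because treating all eligible patients operates only after eligibility is confirmed.

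A reader might infer more than the documents support:
- That the verifier is stated to know the day's status. No sentence says so, and some flow figures are not available.
- That confirmation has no consequence on without-intervention days. The Non-Technical Summary says that handoff outcomes are still assessed then.
- That the ACT clinician, who "will filter out obvious errors from reaching the care team", thereby removes patients from one group. That text concerns delivery of the card. Section 5.3 excludes patients only in the exploratory per-protocol analysis, and only where a card was never accessed.
- That the printed example week 3 shows the ratio being abandoned. It is an example, and section 4.2.2 fixes 60 and 30 days.

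It is also fair to object that randomizing the day order would not hide the status once the day has begun.

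**Conclusion.** The point holds as a limited design weakness that should be addressed. A predictable day status, an unmasked human confirmation step and an undefined intention-to-treat set together allow selection to differ by day type. The documents do not show that it will.

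On assumed inputs the plausible bias is about 1 to 4 points. It reaches 6 points only if half the hard handoffs are lost on one day type with a 45-point outcome contrast, or if 20% of all flagged patients are lost with a 30-point gap. Against the 13.2-point detectable difference at 117/233, 4 points is about 30% (4.0/13.2) and 6 points about 45% (6.0/13.2).

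The conclusion rests on the inference that ACT clinicians know the status. The sizes rest on assumed rejection rates and outcome contrasts.

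**What to change.** (a) Define the with/without comparison set in sections 4.2.3 and 5.3 by the automatic screen, applied identically on both day types. Allow removal only for a coded failure of a listed inclusion criterion, recorded without reference to day status. Apply any threshold change to both day types from the same date.

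(b) Log flagged, confirmed and rejected patients with reasons, and report the counts by day type. Survey flagged patients where possible, so that a sensitivity analysis on all flagged patients can be run. The items that section 4.3.1 lists for storage already include study identifiers, date, time, the intervention indicator and model output. The confirmation decision and its reason would be added.

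(c) Optionally, draw the day order at random by script within 3-day blocks, constrained to keep weekdays balanced. This removes advance predictability but does not mask status on the day, so it supplements (a) and (b) and cannot replace them.

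Cost: an amendment to the wording and a little more logging and survey work. The all-flagged analysis will include some ineligible patients, which dilutes the effect slightly. Option (c) also reduces advance planning of days.

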## 4.3 Interventions

Figure 2 is a flow diagram of the activities during a patient's day and Figure 3 is a patient timeline.

[figure not shown]
[figure not shown]

Figure 3: Patient activity timeline

# 4.3.1 ML Report Card

The core intervention is the ML report card containing predictors of adverse events. Figure 4 is an example of the printed report card on a simulated patient. No personally identifiable information is included, other than a randomized study ID. The report card includes the operating room and date, to allow providers to know that it is for the current patient. Because the printouts are only created in operating rooms and PACU, this is sufficient information to place it in the correct chart. However, at other times the report card itself does not contain sufficient information for anyone without the studyID-patientID mapping file or pre-exising access to the EHR to determine the patient. Operating room number and time is included, but these can not be mapped to patients without the detailed surgical schedule in the EHR. The QR

code study links to an anonymous survey (no patient or provider information) for problems with the report card for the education and testing phase. The evaluation phase survey includes the additional questions in the appendix (triggered on date.

The ML risk profile generated for each patient will include risk of 30 day mortality, pulmonary complications and respiratory failure, acute kidney failure, transfusion, deep venous thrombosis, cardiac complications, and unplanned ICU admission. Additional predicted outcomes may be added based on feedback from healthcare team members. Risk profiles will display the average for all patients undergoing the same surgery, the risks calculated using preoperative assessments only (i.e. excluding intraoperative data), and the end-of-case values (i.e. including preoperative and intraoperative data). Literature-based estimates of probability of postoperative nausea and vomiting and severe postoperative pain will also be included where elevated. Expert-curated summaries of important variables will be included in the Epic report card, which include: estimated blood loss, fluids given, opioids given, duration of anesthesia, antibiotics given. Explanatory tools for the risk profile will also be generated based on SHAP values [Lundberg 2017] identifying the variables with greatest influence on predictions

Figure 4: Example ML report card

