#### Methods note

Risks generated using pre-anesthesia assessment, major comorbidities, laboratory values, and preoperative vital signs; errors in these values can significantly affect the calculations. Risk calculations use gradient boosted decision trees trained on BJH inpatient data 2019-2021. see https://pubmed.ncbi.nlm.nih.gov/31558311/

study ID 86915c307cbd5e01531052a04ff901d94371e8bf

The ACT detects that cases are near completion and that a report card should be triggered in two ways. First, the circulating nurse in each room electronically marks that a room is "close" in the EHR, usually during closure, to ensure that subsequent patients are called to the preoperative area and supplies for the next case are readied. This is performed with high fidelity as it is considered important to prevent case delays. The displayed OR schedule in Epic changes color, making this easily recognized. Second, an algorithm detects when changes in the anesthesia record suggest that the case is concluding. Both of these features cause the ML dashboard in the ACT (Figure 5) to highlight the patient as needing review to validate the report card. After manual validation, the report card will print directly in the operating room and a notification is sent to the circulating nurse to add it to the chart and provide it to the anesthesia team for handoff. The risk profile is then made active in a Best Practice Advisory in Epic.

-	nesthesia Control Tower ML Dash eview." Additional columns not sho			formation reda	acted. Yello	w highli	ght implies
Room Name	Description	akigr1\$	cardiac \$	death_in_3d=	DVT_PE\$	ICU \$	post_dialysis
BJH OR POD 2 ROOM 209	###LAPAROSCOPIC CHOLECYSTECTOMY	2.90%	1.60%	0.10%	8.80%	5.20%	0.10%
BJH OR POD 3 ROOM 301	EXPLORATION LIVER TRANSPLANT WITH WASHOUT LIVER BIOPSY AND BILE DUCT REVISION	67.10%	6.90%	7.60%	1.20%	93.40%	0.90%
BJH OR POD 2 ROOM 211	TRACHEOSTOMY PERCUTANEOUS	40.30%	2.70%	3.50%	7.40%	94.50%	0.20%

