This form is to collect reports of problems with the Al generated risk estimat study PI at [contact] if this doesn't cover your needs. The for does try to link to a patient so that we can figure out what caused the proble appreciate all feedback. The study team will never try to figure out who subn you.	rm doesn't track who you are (it is anonymous) but it em. This is an experiment (IRB: 202103210) and we
This form is to report safety problems with the Al postoperative risk report it does try to link to a patient so that we can determine what happens is approved for HIPAA-protected information.	
This field should auto-populate with a study ID from the link you followed to get here. Otherwise, (1) if you have a QR code with the email me link, and you are at a machine with a barcode scanner, click in the below field and scan the QR code (2) this is a HIPAA-protected portal, you can enter any of the Epic patient IDs and the study team will link it to the correct person.  * must provide value	d46e6e6bb147f7ebdf645e2e9be156172c32897e  Expand
Common problems:	☐ The report card is for the wrong patient ☐ The report card generated on a non-surgical patient ☐ The report card generated too early (preop) ☐ The report card generated too late (not immediately postop) ☐ The risk estimates are too low ☐ The risk estimates are too high ☐ The risk estimates were otherwise confusing ☐ The report card does have / use data that I think it should ☐ The report card has incorrect data ☐ The report card display / formatting was broken
This problem made the report card unsafe  * must provide value	○ Yes ○ No reset
Tell us anything about the problem	
	Expand
If you have comments or suggestions that aren't a problem w	vith the report card, include them here

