#### 6.3 Harms

The postoperative provider survey will include a link and phone number to contact the research coordinator if they believe a serious adverse event or near miss occurred related to the ACT-postoperative communication. As an example, they may believe that ML risk estimates were sent for the incorrect patient. Our communications will all include the role of the ML predictions as advisory, and that the responsibility for decision making lies with the provider. These will be reported to the WUSTL IRB. Descriptive statistics related to uncommon potential harms will be included in the trial reporting.

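### Room and date do not uniquely identify the patient on the printed report card, and no planned step confirms that the paper matches the chart

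*Combined protocol and SAP*

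**What the plan says.** Section 4.3.1 (ML Report Card) sets the identification rule for the paper card. "No personally identifiable information is included, other than a randomized study ID". In place of a name or record number: "The report card includes the operating room and date, to allow providers to know that it is for the current patient". It then concludes: "Because the printouts are only created in operating rooms and PACU, this is sufficient information to place it in the correct chart". A time is printed too, but the section adds: "Operating room number and time is included, but these can not be mapped to patients without the detailed surgical schedule in the EHR". On the example card the time is a generation stamp, shown next to the room.

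The text after the example card's Methods note, still in 4.3.1, describes the trigger. The circulating nurse marks the room as close to finishing, usually during closure, "to ensure that subsequent patients are called to the preoperative area and supplies for the next case are readied". An algorithm reading the anesthesia record is a second trigger. Either one flags the patient for review in the Anesthesia Control Tower (ACT). "After manual validation, the report card will print directly in the operating room", and the circulating nurse is notified to put it in the chart and give it to the anesthesia team. The Epic advisory is then activated.

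The safety survey (Figure 7, section 4.4.1) offers tick boxes for a card belonging to the wrong patient and for "The report card generated too late (not immediately postop". Section 6.3 illustrates a reportable event with the case where providers think that "they may believe that ML risk estimates were sent for the incorrect patient".

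**The concern.** The filing rule relies on two items that successive patients in one room have in common. If validation runs long and the next patient is already in the room, the card passes the stated check for the wrong person. The plan calls the check sufficient and adds no confirmation step, although its own safety survey and harms section allow for late and wrong-patient cards.

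Two things are at stake. The first is patient safety: a receiving team could read another patient's risk profile. The second is data integrity. Sections 4.3.3 and 4.3.1 put a patient-specific survey link on the printout, and Figure 7 shows the study ID filling in automatically from the link. A provider who scans a misfiled card would describe one patient's handoff under another patient's ID.

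**Working it through.** The plan states no figure to reproduce, so the check sets the passages side by side.

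1. **Is the key unique?** The stated key is room plus date. If a room takes *k* cases in a day, the key fits *k* patients and is unique only when *k* = 1. The trigger text speaks of later patients and a next case, so *k* > 1 occurs. The documents give no count per room. The plan's own dashboard (4.3.1) looks up a profile by date, time and room, which is a finer key than the one the filing rule relies on.

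2. **Can the paper appear after the patient has left?** The order is: room marked or algorithm fires, ACT review, print, nurse notified. The review has no stated time limit, and no rule covers a patient who has already gone. The path is open. It does require the review to outlast the rest of closure, emergence, room exit, turnover and the next patient's entry.

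3. **Does the printed time separate the two patients?** There are two cases.
   - Card generated before turnover, printed after: the stamp falls in the first patient's time in the room and separates them, provided someone compares it with the schedule.
   - Card generated after turnover: the stamp falls in the second patient's time in the room and does not separate them.

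   The documents do not say whether generation comes before or after validation. No one is assigned to make the comparison.

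4. **Do other steps confirm the match?** ACT review precedes printing, so it cannot see where the paper goes. The text message to the PACU resident (4.3.3) identifies the OR, not the patient. The study ID is randomized and means nothing at the bedside. Clinical values on the card could be compared with the chart, but no one is asked to do so.

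5. **PACU printing.** Section 4.3.1 says cards are also created in PACU. Section 1 gives a usual stay of 45 minutes to several hours, so two patients from one room on one date could be there together. The same ambiguity applies.

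6. **Effect on the data.** Allocation is by day (4.2.3), and two patients who share room and date share the day. A swapped survey answer therefore stays on a with-intervention day and does not change arm. The damage is at record level: the answer describes the wrong patient, possibly one who is not eligible. For the inaccuracy rate, a noticed mismatch may be counted as wrong content when it is a filing error, and an unnoticed one is not counted. Section 4.5 illustrates precision with 0/150 reports, where a single report moves the observed rate by 1/150 = 0.67 percentage points.

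7. **Volume (4.2.2).** Planned: 350 patients over 90 days, 60 of them with intervention. If spread evenly, 350 × 60/90 = 233 cards, and 350/90 = 3.9 eligible patients per day. The low daily number does not remove the risk, because the patient who wrongly receives a card need not be eligible. Cases per room, turnover time and validation delay are not given, so no misfiling rate can be derived.

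**The case against.** The strongest reply is that the scenario is remote and already cushioned. The trigger usually fires during closure, not at turnover. Section 4.3.1 places ACT communication before formal handoff. The nurse is alerted when the card prints, and would have to file a sheet meant for the PACU signout with a patient whose operation is just starting. Keeping identifiers off the paper is deliberate. The tick boxes and the section 6.3 example are reporting aids, not forecasts, and a late card need not mean one printed after turnover. All of this stands and argues for a low frequency. It does not make room and date unique, and it does not supply a confirmation step.

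Four stronger readings are tempting but not supported:

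- *The intended patient gets nothing.* The Epic advisory is still activated in that patient's own chart; what is lost is the paper.
- *The reader cannot notice the error.* The example card shows weight, laboratory values and comorbidities that can be compared with the chart. The gap is that no such comparison is planned.
- *The intention-to-treat comparison is compromised because the intended patient still counts as treated.* Keeping delivery failures in the assigned group is what that analysis does. Section 5.3 adds a per-protocol analysis that excludes cards never accessed outside the ACT.
- *A definite number of cards will be misfiled.* Assuming that 2% to 5% of 233 cards print after the patient has left gives 4.7 to 11.7. The percentages come from nowhere in the documents. Even if they were right, the result would be at most an upper bound, since an empty room or the last case of the day gives no second patient to match.

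**Conclusion.** The concern holds as a gap in the identification rule. Section 4.3.1's claim that room and date suffice conflicts with its own account of successive cases and untimed validation, and should be reconciled with the safety survey and section 6.3. This rests on two readings: that references to later patients mean more than one case per room per day, and that no matching step exists outside the text available (some figures are not shown).

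The mechanism is supported; the frequency is unknown. The primary between-day comparison is not biased by this route alone. The change is worth making because it is a cheap safeguard against a kind of error the plan itself names.

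**What to change.** In section 4.3.1:

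- Delete the statement that room and date are sufficient for filing.
- Print the scheduled procedure text, which the ACT dashboard already displays, and the case's in-room time if the data feed holds it (the documents do not say that it does).
- Have whoever files the card check these items against the chart, both for cards printed in the OR and for cards printed in PACU.
- Do not print in the OR once the EHR shows that the patient has left. Rely on the Epic version and log the event as a print-delivery failure, so that its frequency becomes known.

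This costs a template line or two, one print condition and a short check by the person filing. Name and record number stay off the paper, as the plan intends. The downsides are slightly more case detail on a sheet that stays in the chart, and late cards reaching staff only through Epic.
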